**The Feasibility, Usability, and Acceptability of Using the Oculus™
Virtual Reality Gaming Technology in Stroke Survivors for Upper Extremity and
Cognitive Rehabilitation**

NCT05672628

Version Date: 03/06/2024

Protocol Title: The Feasibility, Usability, and Acceptability of Using the Oculus™ Virtual Reality Gaming Technology in Stroke Survivors for Upper Extremity and Cognitive Rehabilitation

Principal Investigator: [name]

Co-Investigators: [name], DO; [name]; [name], OT; [name], SLP; [name]; [name] MD

Population: Stroke survivors and caregivers (n= 20 dyads) reflecting a range of stroke subtypes, disabilities, and races/ ethnicities will be recruited.

Number of Sites: 1 – Aging in Place (AIP) apartment, University of Texas Health Science Center at Houston

Study Duration: November 2022 – October 2023

General Information

- Primary Specific Aims (See Figure 1):
 - **S.A.1.** To test the (a) feasibility, (b) usability, and (c) acceptability of using the Oculus VR for chronic stroke survivors (6 months-5 years) who have mild-moderate cognitive and unilateral arm impairment to administer upper extremity and cognitive rehabilitation (n=20 dyads).-
 - **SA 2:** To calculate the change in upper extremity (Fugl-Meyer, ARAT) and cognition (MoCA) scores on standardized measurements per standard of care (n=20 dyads).
 - **S.A.3.** To qualitatively explore the impact of engaging caregivers in supporting the stroke survivor's rehabilitation and the impact of this engagement on the stroke survivor and caregiver dyad using semi-structured interviews. (n=20 dyads).
- Objectives:
 - Our overall objective in this application is first to determine whether Oculus VR is feasible, usable, and acceptable to stroke survivors who have chronic mild-moderate cognitive and upper extremity deficits. Our secondary objective is to explore the impact of the rehabilitation sessions using the Oculus VR on the caregiver-stroke survivor dyad

Background/Significance

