- **A.6 Success of Remote Stroke Rehabilitation Depends on Caregiver Participation for Sustainability.** A significant barrier to stroke survivors accessing rehabilitation is the time burden and travel to appointments due to immobility, geographical distance, and caregiver work obligations.²⁴ During the COVID 19 pandemic, family caregivers of stroke survivors expressed uneasiness when unable to attend rehabilitation appointments due to COVID regulations.²⁵ Remote stroke rehabilitation may effectively address these barriers. Stroke survivors' motivation to engage in rehabilitation sessions has been shown to be positively influenced by positive reinforcement from the rehabilitation therapist.²⁶ Galvin and colleagues found that stroke patients (n=24) who received assistance/ feedback from a family caregiver during inpatient rehabilitation sessions had better motor outcomes than patients in the control group who did not receive input from a family member (n=20; P<.05).²⁷ Family members who participated during inpatient rehabilitation experienced lower caregiver stress than those in the control group (P<.01). Another study demonstrated that persons with dementia whose caregivers assisted with cognitive rehabilitation had improved memory as compared to the

control groups that did not involve caregivers.²⁸ Caregiver participation during rehabilitation may be essential for the sustainability of home-based cognitive and motor rehabilitation outcomes but has not been well-studied.

Population/ Sample Size

- Inclusion Criteria:
 - Ischemic, hemorrhagic, or subarachnoid hemorrhage (SAH) stroke diagnosis within 6 months to 5 years of enrollment. If the participant had a brain aneurysm then it must be secured. MRI report may be requested to confirm diagnosis or deficits as needed. Dyads will be included if they 1) are ≥ 18 years old; 2) can read, write, comprehend, speak English; and 3) are willing and able to provide informed consent. Caregivers must live in the home with the stroke survivor.
- Exclusion Criteria:

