 - Stroke survivors will be excluded if they do not have score ranges that indicate mild to moderate severity on prior post-stroke neuropsychological tests, or the MoCA (15-25) using normative data based on education, age, and other standard demographic data, or other appropriate cognitive screening test selected by the speech language pathologist (also on this application) if the participant has aphasia, hemiopsia, other neurological or specific cognitive deficits, or demographic factors (e.g., education level) that prevents the participant from being accurately examined using MoCA or a modified MoCA; if cognition is within normal range then a FM (20-50), if they are unstable while standing unassisted, have a history of motion sickness/ vertigo/ dizziness/ seizures (a doctor's note will be requested for participants who do not believe their seizures will be triggered by the VR), claustrophobia, blind/deaf, and cannot hold the controller in their affected arm with or without the use of assistance.

Study Design/Methods

[figure not shown]

Figure 1: Study Schema

- Figure 1 depicts the overall study schema or flow as described below.

- Study Overview:
 - **S.A.1.** With the current drive for telerehabilitation and the advent of VR headsets, the examination of human factors perspectives is necessary before full implementation. End user perspectives regarding the impact, perceived usefulness, and perceived ease of use are essential, particularly in the older stroke population.
 - **S.A.2.** The rehabilitation team will measure changes on standardized measurements as part of standard of care.
 - **S.A.3.** Understanding the role of caregiver engagement upon stroke survivor rehabilitation outcomes and its potential impact on the quality of dyadic interpersonal relations is imperative for the sustainability of using VR for stroke rehabilitation in the home.
- Recruitment:
 - We will recruit 20 stroke survivor dyads (n=40) from the
 - Place: UT Physicians Department of Neurology Stroke Clinic, Brain and Behavioral Health Clinic, TIRR, Memorial Hermann, and Stroke Survivor Support Groups. In 2021, the clinic treated approximately 1000 stroke patients. Based on our knowledge of the clinic and previous experiences with stroke trial enrollment, enrolling 20 dyads over a 6-month recruitment period will be feasible. All rehabilitation sessions will take place in the Aging in Place (AIP) apartment.

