 - Subjects meeting inclusion criteria will be offered participation incentives of \$100.00 (\$40 gift cards will be given at the first session and \$60 will be given at the final session) as well as parking reimbursement for each session to take place at the Cizik School of Nursing.
- Pre-Screening and Measurements:
 - Measurement objectives are to (1) determine study eligibility, (2) obtain demographic data, and (3) evaluate acceptability measures (4) assess perceived usefulness, ease of use, and attitude toward using the technology by conducting usability surveys and interviews. The informed consent document and quantitative measures will be available in English and accessible via REDCap.^{30,31}
 - Study personnel will determine if participants are cognitively able to consent by pre-screening participants with the following questions:
 1. *Have you/the participant ever been diagnosed by a doctor with dementia?*
 2. *Think about your/their abilities 10 years ago compared to the day before your/their stroke. Is your/their ability to make decisions on everyday matters better, the same, or worse?*
 - Please see Appendix A for the list of instruments and their psychometric data. See Figure 2 for primary and secondary outcomes and their timepoints.

Intervention

- The AIP apartment (See Appendix B) is a unique lab setting that simulates a real-world apartment. It is well-equipped with cameras to monitor the participant's rehabilitation session and their interaction with the therapist and caregiver and offers a typical living room with a smart television, an ideal setting for proof of concept of using the Oculus VR using the Job Simulator game (Appendix C) for remote stroke rehabilitation.
- Upon successful completion of this research, we expect our contribution to determine the

feasibility, usability, and acceptability of the Oculus VR for stroke rehabilitation in chronic stroke patients.

- This contribution is innovative because to the best of our knowledge no studies have evaluated the use of the Oculus VR in stroke patients stroke rehabilitation.
 - The Oculus VR engages two brain domains simultaneously and this may prove to be a novel and effective form of stroke rehabilitation.
- Our intervention has been developed in partnership with experienced stroke rehabilitation experts so that it can be easily implemented in any setting.

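### The only decision-making question in the capacity pre-screen compares two times before the stroke, so the pre-screen can flag post-stroke loss of capacity only through a formal dementia diagnosis

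*Combined protocol and SAP*

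**What the plan says.** The section Pre-Screening and Measurements gives the two questions a single purpose: "Study personnel will determine if participants are cognitively able to consent by pre-screening participants with the following questions". Question 1 is "Have you/the participant ever been diagnosed by a doctor with dementia". Question 2 opens with "Think about your/their abilities 10 years ago compared to the day before your/their stroke" and then asks "Is your/their ability to make decisions on everyday matters better, the same, or worse". The section does not say what any answer leads to.

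Three other parts of the protocol bear on the point.

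- **Timing.** The inclusion criteria require a "stroke diagnosis within 6 months to 5 years of enrollment".
- **Population.** The first specific aim describes survivors "who have mild-moderate cognitive and unilateral arm impairment". Under the exclusion criteria, the cognitive routes into the study are earlier post-stroke neuropsychological tests, a MoCA of 15 to 25, or an alternative test chosen by the speech language pathologist. People with normal cognition can enter on a Fugl-Meyer score of 20 to 50.
- **Consent.** Dyads must be people who "are willing and able to provide informed consent". Appendix Q begins with a baseline visit whose purpose includes making sure that the participant understands the study. Cognitive testing is listed after it.

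**The concern.** A capacity check has to address the person's ability at the time of consent. Here the item that asks about decision-making stops the day before the stroke. Many of the people the trial seeks have cognitive deficits that are measured after the stroke, and that is the period the item leaves out. Someone whose decision-making was steady up to the stroke and poor since could truthfully answer that it was the same.

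What is at stake is participant protection and the meaning of the inclusion criterion on consent. Sessions are recorded on camera, and participants need to understand that they may stop. The protocol also expects this study to lead to randomised trials, which could inherit the same screen.

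**Working it through.** No sample size, power or error rate is involved. The check is date arithmetic, followed by a comparison of what each safeguard covers.

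**Inputs**

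- Time from qualifying stroke to enrolment, *t*: 0.5 to 5 years (Inclusion Criteria).
- Earlier time point in question 2: 10 years before screening.
- Later time point in question 2: 1 day before the stroke.
- Assumption: screening and enrolment are close together, so 10 years can be counted back from enrolment.

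**Where the earlier time point falls**

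Years before the qualifying stroke = 10 − *t*

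- Longest time since stroke: 10 − 5 = 5 years before the stroke.
- Shortest time since stroke: 10 − 0.5 = 9.5 years before the stroke.

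The result is positive across the whole eligible range, so the earlier time point always precedes the qualifying stroke. The later one does so by definition. Question 2 covers none of the 0.5 to 5 years since the stroke.

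Prior strokes do not rescue the item. If a participant takes the wording to mean an earlier stroke, the day before it lies further back still.

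**What each safeguard covers**

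| Element | Covers the time after the stroke? | Stated method or consequence |
|---|---|---|
| Question 1, dementia diagnosis | Yes, but only through a doctor's diagnosis | No consequence stated |
| Question 2, everyday decisions | No | No consequence stated |
| Inclusion criterion on consent | Yes, in principle | No method beyond the pre-screen |
| Baseline consent visit, Appendix Q | Yes, in principle | No tool, threshold or specific item to record |
| MoCA or alternative test | Yes | Used for eligibility and outcome, listed after consent, not described as a capacity check |

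**Three cases, followed through both questions**

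- Decision-making steady until the stroke, poor since, no dementia diagnosis: question 1 no, question 2 the same. Nothing is flagged.
- Dementia diagnosed after the stroke: question 1 yes. Flagged.
- Decision-making worse over the years before the stroke: question 2 worse. Flagged, but on past change and not on present ability.

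The first case is the gap. It includes undiagnosed impairment and loss of capacity that is not dementia.

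**The case against.** The strongest reply is that these two questions are only a first filter. Ability to comprehend English and ability to consent are separate inclusion criteria. The baseline visit is meant to secure understanding and has a sign-off column. Current cognition is tested by the first session, with a speech language pathologist choosing the test where the MoCA is unsuitable. The guided cues in Appendix E ask whether the participant understands what is being asked and how they would signal to stop. All of this shows that present understanding is not ignored. However, none of it names a check of capacity at the point of consent, and both the cognitive testing and the cues come after consent. The sponsor may also say that question 2 was meant to pick up decline before the stroke. The text does not say so, and if that was the aim, no question addresses present decision-making.

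Four stronger readings are tempting, and the documents do not support them.

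- A reader might infer that the whole pre-screen misses the post-stroke period. Question 1 has no time limit and can pick up dementia diagnosed after the stroke.
- A reader might infer that all 20 survivors are equally affected. Normal cognition is admitted by the Fugl-Meyer route, and the concern is weaker for those people.
- A reader might infer that a MoCA of 15 to 25 implies inability to consent. Nothing in the protocol says so. Impairment and incapacity are different things.
- A reader might infer that the SUS, PQ and SSQ data are weakened. Ability to consent is not the same as ability to answer a questionnaire, and no text links them.

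The objection also bears on the remedy. A question about change from before the stroke to now, used as a gate, could exclude people with mild impairment who can still consent. That part stands.

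**Conclusion.** The point holds in a limited form. For every eligible participant, both times in question 2 precede the qualifying stroke, by 5 to 9.5 years and by one day. The only decision-making item therefore cannot register post-stroke decline, and the pre-screen can flag post-stroke loss of capacity only through a dementia diagnosis. This goes beyond missing detail: a stated procedure does not do the job it is given, in a study that largely seeks people with current cognitive impairment.

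The number of people who might consent without adequate capacity cannot be derived from the documents. No estimate, test or sample size changes.

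The conclusion rests on two conditions. One is that ten years is counted back from about the time of enrolment. The other is that no further capacity procedure exists in the consent pages, which were not available for review. If there is one, the practical gap is smaller, but question 2 still needs rewording.

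**What to change.** 1. Reword question 2 to ask about current everyday decision-making.
2. State what each answer to both questions leads to. Treat a reported difficulty on question 2 as a prompt for closer assessment, not as automatic exclusion, so that the intended population is not screened out.
3. Make the consent decision rest on a short teach-back at the existing baseline consent visit, in which the participant explains the study's purpose, its voluntary nature and the right to stop. Record it as a line in Appendix Q.

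The cost is protocol wording and a few minutes per participant at a visit that already takes place. Some additional screen failures are possible; their number cannot be derived. If the consent pages already describe such a check, a cross-reference from Pre-Screening and Measurements would replace step 3.

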- We believe that this study will generate an estimate of the effect that can be used to inform the development of randomized controlled studies (RCTs).
 - This study will also generate RCTs examining the use of the Oculus VR as a form of stroke rehabilitation that is scalable to the participant's home setting.
 - There are few studies that have examined the role of caregiver engagement on the success of remote stroke rehabilitation.
- The caregiver will be encouraged to use Caregiver Cues (Appendix D) as this will help the caregiver to engage with the participant using encouragement or positive cues to the stroke participants to support them during the session.
- The therapist or RA (who will be trained by the therapist) who is conducting the session will use the Therapist Guided Cues (Appendix E) to guide the stroke participant with problem solving and planning for performing home exercises that will be provided to the participant at the first session.
- The data we obtain from caregivers and stroke survivors (dyads) will inform future studies that examine ways to best support the dyads to improve stroke rehabilitation outcomes and reduce stress in the caregivers. (See Appendix F)

Statistical Analysis

- To address S.A.1., feasibility, usability, and acceptability of the Oculus VR headsets for upper extremity and cognitive therapies will be analyzed as follows: Feasibility: Assessed from the number sessions attended and time spent using the Oculus VR. The minimum number of sessions expected for a user are 2 per week (8 sessions) and the minimum time spent playing Job Simulator is 1 hour per week (4 hours) through the end of the study. Descriptive statistics of the participation rates and measures including frequencies, median and interquartile ranges for sessions attended and time spent using the game. Usability: Descriptive statistics for demographic and clinical data and participant scores on the SUS and PQ will be calculated. (See Appendix G and H) We will refrain from using inferential statistics since this is a pilot study and hypothesis testing is not the objective. Acceptability: Descriptive statistics for scores on the SSQ will be calculated at baseline and after each session (See Appendix I). We will examine the trend of symptoms for each participant.)

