- To address S.A.2. As part of standard of care, we will calculate change in arm and cognitive scores for each stroke participant from the following tests: MoCA, FM, and ARAT. (See Appendix J, K, and L) After inspection of the distribution, either the paired t-test or the nonparametric Wilcoxon signed rank test will be used to evaluate the significance of the difference score. However, statistical inference is not the primary interest of this pilot study. The effect size provided by Cohen's d measure, i.e., the standardized difference of mean score, will provide a preliminary measure of the effectiveness of Oculus VR in this pilot study. Similarly, standardized differences in the BSFC-s scores will provide the effect sizes for the change in caregiver burden.
- To address S.A.3., interview data will be analyzed following methods for thematic analysis.^{34,35} Using a qualitative data analysis program, Atlas.ti,³⁶ 2 researchers will review transcripts to gain a sense of the whole, identify codes, categories, and generate higher order themes to describe

the role of caregiver engagement during the session. Reasons for non-participation will be obtained from those eligible participants who decline participation. Unacceptable components and reasons for non-participation will be considered in the planning and designing of future trials.

Outcomes

- Upon completion of these aims, the expected outcomes are to develop randomized control trials (RCTs) to determine the effectiveness of the Oculus VR for stroke rehabilitation. We anticipate using the information from the dyadic interviews to develop qualitative studies and RCTs examining the role of the caregiver on remote stroke rehabilitation outcomes.
- Please see Table 1 (below) for the outcomes with timepoints.

Primary and Secondary Outcomes with Timepoints			
Primary	Timepoint	Secondary	Timepoint
MoCA (Appendix J)	Baseline and Last Session	Pre-Intervention Questionnaire (Appendix R)	Baseline Session
Fugl-Meyer (Appendix K)	Baseline and Last Session	Therapy Follow-Up Checklist (Appendix M)	Session 2 – Last Session
ARAT (Appendix L)	Baseline and Last Session	Post-Intervention Questionnaire (Appendix S)	Last Session
Caregiver Burden Scale (for caregiver only; Appendix F)	Baseline and Last Session		
Simulator Sickness Questionnaire (Appendix I)	Session 1 – Last Session		
System Usability Scale (Appendix G)	Last Session		
Presence Questionnaire (Appendix H)	Last Session		

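### S.A.2 tests three primary-labelled change scores for significance although S.A.1 gives a study-wide reason against testing, and the effect size meant for trial planning has no interval

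*Combined protocol and SAP*

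**What the plan says.** The Statistical Analysis section handles the aims one at a time.

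- **S.A.1, Usability item.** The plan is descriptive: "Usability: Descriptive statistics for demographic and clinical data and participant scores on the SUS and PQ will be calculated". The next sentence is "We will refrain from using inferential statistics since this is a pilot study and hypothesis testing is not the objective". The Acceptability item follows.
- **S.A.2.** The plan is that "we will calculate change in arm and cognitive scores for each stroke participant from the following tests: MoCA, FM, and ARAT". On the test it says: "After inspection of the distribution, either the paired t-test or the nonparametric Wilcoxon signed rank test will be used to evaluate the significance", meaning that of each change score. It then adds "However, statistical inference is not the primary interest of this pilot study", and says that Cohen's d "will provide a preliminary measure of the effectiveness of Oculus VR in this pilot study".
- **Caregiver burden (BSFC-s).** A standardised difference is planned. No test is named.
- **Table 1.** MoCA, Fugl-Meyer, ARAT and caregiver burden all stand in the Primary column.

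The plan gives no significance level, sidedness, multiplicity rule, rule for choosing between the two tests, or confidence interval. The Intervention section expects the study to produce an effect estimate that can inform randomised trials.

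**The concern.** The S.A.1 sentence gives two reasons for avoiding inference: the study is a pilot, and testing hypotheses is not its aim. Both are true of the study as a whole. An analyst cannot tell from the text why they bar a test on a usability score but allow one on MoCA.

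Three consequences follow.

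1. **p-values on primary-labelled outcomes.** The protocol's closing plans, just before the References, include showing that the technology can improve arm movement and cognition, with grant applications to follow. A small p-value would be easy to use for that purpose. The design cannot support it: there is no control group, home exercises are given out at the first session, and Appendix M logs outside therapy. The MoCA used for eligibility also serves as baseline, so some regression to the mean is possible. A test of zero change is not a test of benefit from VR.
2. **No measure of precision.** An effect size without an interval does not tell the planner of a randomised trial how uncertain it is.
3. **A possible mismatch.** If skewness leads to Wilcoxon, the p-value comes from ranks while the reported effect size stays mean-based.

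**Working it through.** **Inputs.** From the documents: 20 dyads, so at most 20 paired differences per score; three tested scores (S.A.2). Assumed, because the plan is silent: two-sided 5% per test, all 20 pairs complete, and Cohen's d standardised by the SD of the differences. The plan states no error rate or power, so there is no figure to reproduce.

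**1. Chance of at least one false positive across three tests.**
- Independent: 1 − 0.95³ = 1 − 0.857 = 0.143. Upper bound: 3 × 0.05 = 0.15.
- Correlated, from simulating three paired t statistics at n = 20 with 40,000 runs: 0.138 at correlation 0.3, 0.124 at 0.5, 0.111 at 0.7 and 0.086 at 0.9.

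Fugl-Meyer and ARAT both measure the arm in the same people, so full independence is unlikely. The range is about 9% to 14%.

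**2. Does choosing the test from the data add error?** A Shapiro-Wilk pre-test stands in for the unspecified inspection (n = 20, 10,000 runs per row, true mean change zero). Entries are rejection rates.

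| Distribution of differences | t-test only | Wilcoxon only | Chosen by pre-test |
|---|---|---|---|
| Normal | 0.049 | 0.045 | 0.049 |
| Heavy-tailed, t(3) | 0.044 | 0.049 | 0.051 |
| Skewed, shifted exponential | 0.084 | 0.129 | 0.131 |

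Under symmetry the choice costs almost nothing. Under strong skew the excess comes from the skewness: Wilcoxon alone gives nearly the same rate as the chosen test.

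**3. Do the p-value and the effect size match?** The skewed row shows that they may not. The mean change is zero, so the population Cohen's d is zero, yet Wilcoxon rejects 12.9% of the time because its null is symmetry about zero rather than a zero mean. Skew is plausible here. The criteria let people with normal cognition enter on their Fugl-Meyer score, and Appendix J puts normal MoCA at 26 or more out of 30, so such a person can gain at most 30 − 26 = 4 points.

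**4. Precision of the effect size.** An observed d of 0.5 gives t = 0.5 × √20 = 2.236 on 19 degrees of freedom. Solving the noncentral t distribution for the two limits and dividing by √20 gives a 95% interval of about 0.03 to 0.96. For d = 0.3 the interval is about −0.15 to 0.74.

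**5. Power of the paired t-test at n = 20.** 0.25 at d = 0.3, 0.56 at d = 0.5, 0.72 at d = 0.6 and 0.80 at d = 0.66.

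**The case against.** The best reply is that the sentence in S.A.1 is local. It sits between the usability and acceptability analyses, and S.A.2 has its own paragraph and its own stance: tests are run, but inference is said not to be the main interest and Cohen's d is put forward as the measure. **This stands in part.** A reader might infer that the plan forbids inference throughout and then breaks its own ban. The placement of the sentence and the S.A.2 disclaimer do not support that. What remains is a reason worded for the whole study but applied to one aim, and a disclaimer that neither removes the tests nor calls them exploratory.

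The second reply is that both tests are named in advance and that choosing between them on shape is conventional. **This stands.** Step 2 shows almost no inflation from the choice itself; what is missing is the decision rule.

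The third reply is that confidence intervals are themselves inferential: a t-based 95% interval excludes zero exactly when the paired t-test gives p < 0.05, and adding BSFC-s makes four intervals. **This is correct**, and the fix must say how the intervals are to be read. It does not make the bare effect size adequate. Keeping one prespecified test, labelled exploratory, would also settle the inconsistency, but it would leave the effect size without an interval.

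**Conclusion.** The point holds as an inconsistency of rationale between two aims, joined to a gap in reporting. S.A.2 would yield three p-values on primary-labelled scores that the S.A.1 reasoning gives no ground for, and no interval for the estimate meant to inform later trials. The joint false-positive chance is about 9% to 14%, assuming two-sided 5% tests and correlations from 0.9 down to 0. The interval of 0.03 to 0.96 for an observed d of 0.5 assumes 20 complete pairs and standardisation by the SD of the differences.

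Two further inferences should not be drawn. BSFC-s is not a fourth test, since only an effect size is planned for it. Nor would most changes below d = 0.66 be missed: power is 0.56 at d = 0.5 and 0.72 at d = 0.6. The results stay computable and S.A.2 already plays inference down, so this is a change worth making rather than a flaw that undermines the study.

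**What to change.** In S.A.2, replace the significance-test sentence with prespecified estimation for MoCA, Fugl-Meyer, ARAT and BSFC-s:

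- Report mean change and Cohen's d, each with a 95% confidence interval, whatever the distribution looks like. State which SD standardises d.
- Report median change with a bootstrap or sign-test-based interval as a fixed check. With 20 pairs the sign-test interval runs from the 6th to the 15th ordered difference, with coverage 1 − 2 × 21,700/2²⁰ = 0.959. A Hodges-Lehmann interval is less suitable, because it targets the pseudomedian, which equals the median only under symmetry. The check is needed because under the strong skew of step 2 the t-based interval covers only about 1 − 0.084 = 0.916.
- State that the intervals describe precision, are unadjusted for multiplicity, and are not tests of VR benefit in this uncontrolled study.

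In S.A.1, limit the sentence to hypothesis testing so that it agrees with intervals in S.A.2.

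The cost is wording only, with no added data or visits. The downside is that there is no p-value to quote in grant applications.
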